Developing and Testing the Enhancing Active Caregiver Training (EnACT) Intervention for
Dementia Family Caregivers

NCT# 04920006
Protocol/Research Manual of Operations
7/20/2025

University of Utah

Principal Investigator Contact Info:

[name]
College of Nursing
University of Utah
[name]
[name]
[contact]

Study Aims

Aim 1: Develop and iteratively refine the EnACT intervention for ADRD caregivers.

This protocol is for Aims 2 and Aim 3 which is the clinical trial portion of the study:

Aim 2: Evaluate the feasibility and acceptability of the EnACT intervention.

Aim 3: Examine potential mechanisms of change over time and their subsequent impact on proximal and distal outcomes.

Study Design

This is a Stage 1b pilot study to test the feasibility and acceptability of the EnACT intervention. We will use a randomized waitlist control design. Participants will be randomly assigned to one of two groups. All participants will have a baseline measure (week 0), and a Pre timepoint (week 2). Group A will first participate in the intervention (three meetings offered every 2 weeks at Weeks 2, 4, and 6), followed by 8 weeks of follow-up. T1 will be a pretest gathered at enrollment. Group B will wait 8 weeks and then start the intervention at Weeks 8, 10, and 12, with a post-test at Week 14. Data will be gathered at six time points no less than 2 weeks apart over the course of the control, intervention, and follow up. A postintervention debriefing focus group will occur in Week 8 for Group A and Week 14 for Group B to gather feedback on the process and activities and any recommendations participants have for improving the intervention.

Sample Size

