Sample Size/Power Analysis: We will recruit 30 dementia caregivers from the community. Participants enrolled will be randomly assigned to the group-based EnACT intervention ($n = 15$) and a waitlist control group ($n = 15$). As an NIH Stage 1b pilot study, the goal is to assess the plausibility of this work in order to guide the next stage of research. Thus, it should not be expected that the sample size will have outstanding power. Constrained longitudinal data analysis will be used on the data set ($N = 30$) to exploit randomization and integrated with the full longitudinal impact data to give greater power than more limited analyses. Simulations conducted in SAS and analyzed under the integrated model yield a respectable power of .70 against the null hypothesis when the hypothesized slope difference corresponds to a medium effect size of .5.

Sites

The intervention will take place at locations associated with our community partners' caregiver support groups, including senior centers, the Division of Aging & Adult Services, and offices of the Utah Chapter of the Alzheimer's Association. This includes online synchronous platforms such as Zoom.

Eligibility

Inclusion Criteria:

Persons providing primary, informal, support to family members with Alzheimer's disease or related dementia (ADRD). These individuals are 18 and older, and the ability to read and speak English.

Exclusion Criteria:

Formal caregivers, persons under the age of 18, and individuals who have English fluency ratings of *none* or *poor* will be excluded.

Recruitment

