Baseline Assessment (T1): Demographics, Imagined Interactions, Capacity to Adapt, Caregiver Capacity to Appraise Demands, Perceived Stress, Caregiver Well-being

Survey Assessment (Week 2 (T2), Week 5 (T3), Week 8 (T4), Week 11 (T5), Week 14 (T6): Imagined Interactions, Capacity to Adapt, Caregiver Capacity to Appraise Demands, Perceived Stress, Caregiver Well-being

Measures

Feasibility: number screened and enrolled, retention rates, levels of engagement, intervention delivery, assessment-protocol duration, and completion rates

Acceptability: satisfaction with intervention, audio/video documentation of intervention meetings, post-intervention focus groups

Focus Groups: questions on suggestions for improvement, preference compared to other programs they've experienced, barriers to or benefits of use.

Demographics: age, education, gender identity/sexual orientation, race/ethnicity, employment, salary, caregiving experience, frequency of theatre attendance, care-recipient relationship, caregiver support, time as caregiver, type of caregiver, sex and age of care partner, participation in caregiver training or support, type of caregiver training/support, frequency of caregiver training/support, activity/hobbies and frequency of participation.

Imagined Interactions: *Survey of Imagined Interactions* (7-point Likert scale questions) measures outcomes of imagining interactions, including four subscales: *Specificity* (5 items), *Discrepancy* (7 items), *Proactivity* (3 items)

Capacity to Adapt: *Resilience Scale* (7-point Likert scale questions) measures one's ability to adapt, specific to constructs of meaning, self-confidence, perseverance, serenity, and loneliness (25 items)

Caregiver Capacity to Appraise Demands: *Revised Caregiving Appraisal Scale* (RCAS; 5-point Likert scale questions) asks ADRD caregivers to assess the following five subscales: *Burden* (9 items), *Satisfaction* (6 items), *Mastery* (4 items), *Demand* (3 items), *Impact* (3 items)

Perceived Stress: *Perceived Stress Scale* (5-point Likert scale questions) measures self-reported stress (10 items)

Caregiver Well-being: *Modified Caregiver Burden Inventory* (CBI; 5-point Likert scale questions) 24 items comprising five subscales: *Time*, *Physical*, *Social*, *Emotional*, *Developmental*. *Positive Aspects of Caregiving Scale* (PAC; 5-point Likert scale questions) measures the perceptions of the benefits of caregiving (9 items.)

Data Collection and Management

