Descriptive statistics will be used to describe screening, recruitment, enrollment, retention, completion rates, and satisfaction survey results. Qualitative data will be analyzed based on each construct of feasibility and acceptability. NVivo software will be used to organize qualitative data analysis and document an audit trail. Digital audio recordings will be professionally transcribed. Video and written documentation will be directly imported and analyzed in the software. Data will first be coded using these constructs as a priori codes. Then within each code, pattern coding will be used to group data to facilitate descriptions of the screening, recruitment, and enrollment process. In addition, we will use qualitative data to describe reasons for attrition, engagement, satisfaction with the intervention, and intervention delivery. The PI and RA will meet weekly to analyze data, and monthly with the larger team to resolve conflicts in coding and to group patterns into major themes. The use of both quantitative measures and qualitative observations will allow for a rich, in-depth description of both feasibility and acceptability of this intervention.

Feasibility of Outcome Measures

Seven instruments (demographics, *The Survey of Imagined Interactions*, *Resilience Scale*, *The Revised Caregiving Appraisal Scale*, *Perceived Stress Scale*, *Modified Caregiver Burden Inventory*, and *Positive Aspects of Caregiving Scale*) will be used to assess potential outcomes associated with the theoretical framework for this study. Participants in Stage-1b will take the demographic questionnaire at time one and the other instruments at all 6 timepoints. We will gather data on the duration of these tests, proportion completed, and the burden associated with these measures at each timepoint. This will include documenting retention rates, timepoint completion rates, length of intervention meetings, the amount of time to complete measures, and field notes regarding reactions to taking the battery.

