Descriptive statistics—including frequency counts, percent distribution, range, mean, median, and standard deviation—were calculated for all variables and timepoints. Descriptive statistics will be reported for the full sample ($n = 30$), and then for the immediate ($n=15$) and wait-list ($n=15$) groups. We will conduct independent samples statistics (chi-square, Fisher's exact test, Student's t test, and Mann–Whitney tests), as appropriate, to statistically compare immediate to wait-list groups for baseline equivalency. We will use generalized linear categorical dose-response models where the effect of intervention over time on the main and secondary outcomes are estimated. Specifically, the regression controls for baseline measures and defines and estimates two separate parameters: D1, natural change at week 8 and D2 the additional impact of the intervention at week 8. The null hypothesis of natural benefit in the waitlist at 8 weeks (D1) is defined as $D1 = 0$. The null hypothesis of no additional benefit of the intervention is $D2=0$ for week 8 (intervention) and week 14 (end of intervention phase in waitlist control). The overall intervention change is defined as the linear combination of $D1+D2$. Importantly, this

framework allows the change in outcomes in the waitlist control during their active intervention phase to contribute to the estimate of D2 which is advantageous for the current smaller sample size. All alphas will be set at 0.05 but the focus will be to examine the direction and magnitude for promising trends to be validated in a future fully powered study. Estimation is done with maximum likelihood and we will report 95% lower and upper confidence intervals.

Handling of Missing Data

Using maximum likelihood estimation, we will use all available data for analysis. This allows us to reduce bias in the estimation. The maximum likelihood estimates given the observed data points are the values most likely to have generated the complete ensemble of observed sample data under the assumed model. Missing data patterns will be examined and imputation if assumption of missing at random is not rejected may be considered in the presence of significant amount of missing data.

Ethical Issues

Ethical Considerations

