Planned analyses are distinct for Aims 1, 2 and 3. Aim 1 has a unique sample, design, and planned analysis, while Aims 2 and 3 share a sample, design and planned analysis. All three aims of the study are important parts of stage 1 intervention development activities. Aim 1 provides data for Stage 1A (intervention development and refinement) and Aims 2 and 3 provide data for Stage 1B (feasibility and pilot testing). As described in the previous section, we have developed study protocols to ensure participant safety for each aim of the study. Although we will conduct the analyses for each aim as that aim is completed, we do not have any rules, based on those interim analyses, for stopping the study overall.

Data Safety and Monitoring

This project represents stage-1 development activities for a behavioral intervention. As such, it does not constitute an NIH-defined phase III clinical trial. Nor does the study design involve multiple field sites. Lastly, the EnACT intervention and the planned design is considered minimal risk. **Thus, this study does NOT require a data and safety monitoring board.**

Ultimately, the PI, will monitor participant accrual and retention and audit data quality, particularly examining levels of missing data. The PI is ultimately responsible for maintaining the integrity and quality of all study data under the guidance of primary mentor. Data audit reports will be reviewed quarterly to monitor progress and quickly identify and address potential problems. To assist in data and safety monitoring, a “data and safety monitoring” committee will meet to review progress. Safety reports will be submitted to this committee twice a year, and include a detailed analysis of study progress, data and safety issues.

Protocol: EnACT RCT

Version: 7/20/2025

As a general principle, this committee is responsible for developing all protocols that ensure confidentiality and safety of study participants, and then monitoring that those protocols are being practiced by all study staff at all times. Particular responsibilities of this committee include:

- To provide initial and ongoing training to all study staff related to participant safety and data security*
- To review quarterly-generated accrual reports to ensure that sample targets are being met for each Aim of the project

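### The second half of Aim 3, the later effect of mechanisms on outcomes, has no planned analysis, and the planned group-effect models cannot supply one

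*Combined protocol and SAP*

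**What the plan says.** Study Aims gives Aim 3 two parts: how potential mechanisms change, and what those mechanisms then do to outcomes ("Examine potential mechanisms of change over time and their subsequent impact on proximal and distal outcomes"). It is one of two aims that this document covers.

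The model paragraph of the analysis section (under Feasibility of Outcome Measures) plans "generalized linear categorical dose-response models where the effect of intervention over time on the main and secondary outcomes are estimated". It adds that "the regression controls for baseline measures and defines and estimates two separate parameters": D1, natural change at week 8, and D2, the additional effect of the intervention. The null D2 = 0 is stated "for week 8 (intervention) and week 14 (end of intervention phase in waitlist control").

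Sample Size/Power Analysis names a second model: "Constrained longitudinal data analysis will be used on the data set", with power quoted for a slope difference.

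Interim Analysis says that "Aims 2 and 3 share a sample, design and planned analysis", so no separate Aim 3 analysis sits elsewhere.

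On the measures, Feasibility of Outcome Measures says that the instruments "will be used to assess potential outcomes associated with the theoretical framework for this study". Apart from demographics, every instrument is given at all six timepoints. Assessment Schedule sets these at baseline and then "Survey Assessment (Week 2 (T2), Week 5 (T3), Week 8 (T4), Week 11 (T5), Week 14 (T6").

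**The concern.** The second part of Aim 3 concerns a relation between two scores: does a participant's level or change on a mechanism carry through to a later outcome? Every planned parameter is instead a relation between the intervention and a score. The words mechanism, proximal and distal are not attached to any instrument, and the model paragraph's main and secondary outcomes are not named, so these roles could be assigned after results are seen.

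The risk is one of interpretation. If D2 is favourable on, say, imagined interactions and also on perceived stress, it is natural to read the pair as support for a mechanism and to carry that into the larger trial that this pilot is meant to guide. The planned estimates would not justify that reading.

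**Working it through.** **1. The plan's own figure.** The only stated power is 0.70, for a slope difference of effect size 0.5 with 15 per group. A plain two-group comparison gives 0.28 (normal approximation, two-sided 0.05). A D1/D2 model with a constrained baseline gives 0.72 at an assumed within-person correlation of 0.8 (three waves) and 0.73 at 0.6 (six waves). The documents give no correlation, so 0.70 can be neither confirmed nor refuted. It concerns a group effect, not a mechanism-outcome link, and nothing below depends on it.

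**2. Each part of Aim 3 against the plan.**

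| Part of Aim 3 | Needed | Planned |
|---|---|---|
| Change in potential mechanisms | Group and time effects on mechanism scores | D1 and D2, or slope difference, on those scores |
| Later effect of mechanisms on outcomes | Mechanism score as predictor of a later outcome | None |
| Which score plays which role | A list | None; grouped by construct in Measures |

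**3. Can D2 on each score stand in for the link?** Let Z be arm, M a mechanism and Y an outcome, in standardised units (assumed values, week-8 data, 15 per arm):

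M = aZ + e₁, and Y = c′Z + bM + e₂, with within-arm variance 1 for each.

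The intervention effect is a on M and c′ + ab on Y. Take a = 0.5.

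- Full mediation (b = 0.5, c′ = 0): effect on Y = 0 + 0.5 × 0.5 = 0.25.
- No link (b = 0, c′ = 0.25): effect on Y = 0.25 + 0.5 × 0 = 0.25.

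The standard error of either arm difference is √(2/15) = 0.365 in both cases. A simulation of 20,000 replicates agrees: mean effects of 0.50 on M and 0.25 on Y under both truths, with SDs of 0.36 to 0.37. Only a model with M as a predictor of Y separates them (mean b of 0.50 against 0.00). The ambiguity lies in what is estimated, so more participants would not remove it. This illustration has no unmeasured common cause of M and Y; in real data b could be confounded, because M is not randomised.

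**4. Do the data permit a time-ordered analysis?** Sessions are at weeks 2, 4 and 6 in Group A and weeks 8, 10 and 12 in Group B (Study Design). The week-5 survey comes after A's second session and before its third, while B is still waiting. Mechanism at week 5 and outcome at week 8 are therefore time-ordered, with an untreated comparison, provided that B's week-8 survey precedes its first session that week. D1 as defined already assumes this.

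**5. How precise would a link estimate be?** For a partial correlation r with n = 30 and k = 3 covariates (week-2 mechanism, week-2 outcome, arm), the 95% interval is tanh(atanh r ± 1.96/√(n − k − 3)), with half-width 1.96/√24 = 0.400 on the z scale. The documents give no r, so a range is shown, with complete data:

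| Assumed r | 95% interval |
|---|---|
| 0.20 | −0.19 to 0.54 |
| 0.40 | 0.02 to 0.68 |
| 0.60 | 0.28 to 0.80 |

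In the step 3 simulation model with c′ = 0, power to find both a and b significant is 0.09 (a = 0.5, b = 0.3), 0.20 (0.5, 0.5), 0.44 (0.8, 0.5) and 0.56 (0.8, 0.7). Such an analysis can only be exploratory.

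**The case against.** The strongest reply is that this is a pilot. Statistical Management & Analysis says that pilots cannot test hypotheses definitively, the primary goal is feasibility and acceptability, and the model paragraph looks for direction and magnitude only. With power of 0.09 to 0.56 in the illustration, leaving out a mediation analysis is defensible. That stands as a reason not to demand one. It does not supply an analysis for a stated aim; if the link is not to be analysed, the aim should not promise it.

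A second reply is that the Potential Benefits text restates the aim so that the later impact may belong to the training rather than to the mechanisms. On that reading, D2 on stress and well-being scores is the intended estimate. The wording there is ambiguous, but in Study Aims the plural pronoun refers to the mechanisms. The two passages should be aligned.

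Three stronger readings are tempting and are not supported.

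- A reader might infer that Aim 3 as a whole has no analysis. D1 and D2 on the mechanism scores address its first half.
- A reader might infer that the mid-intervention surveys are discarded. The missing-data section uses all available data, and the power section refers to the full longitudinal data. Weeks 5 and 11 may well enter the likelihood; what is missing is any stated hypothesis that uses them for time order.
- A reader might infer that the D1/D2 regression is the only model, or that it is expressly fitted score by score. The power section names another model, which also yields only a group effect, and separate fitting is inferred from the form of the regression.

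Finally, no passage says that parallel effects will be reported as a mechanism. That is a foreseeable misreading, not a planned one.

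**Conclusion.** The point holds for the mechanism-to-outcome half of Aim 3. Followed exactly, the plan produces no estimate of that link, and its group effects are compatible equally with full mediation and with none. This rests on the documents' own text; the simulated values only illustrate it. The design is not the obstacle, since the scores will exist in the right time order. The size is one unanswered clause in one of two aims. Aim 2, the randomised group comparisons and the stated power are untouched. The sponsor should correct it before analysis, and it is cheap to correct.

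**What to change.** Either of two changes closes the gap.

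(a) Restate Aim 3 as estimating D1 and D2 on mechanism scores and on outcome scores, with no conclusion about the effect of one on the other, and align the Potential Benefits wording. This costs only text.

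(b) Before analysis, list which scores are mechanism, proximal and distal, and name one or a few mechanism-outcome pairs. Six instruments are repeated, so splitting them into mechanisms and outcomes gives 5 (1 × 5) to 9 (3 × 3) pairs even before subscales; without a named short list the choice is open. For each pair, fit an exploratory lagged model in both arms: week-8 outcome on week-5 mechanism, adjusted for the week-2 values of both and for arm. Group B's waiting period is then the untreated comparison. Group B's week 11 to week 14 data can be shown as supplementary. Report estimate and interval only. State that the link is a non-randomised association open to confounding, and that week 5 falls before Group A's third session, so the mechanism is measured at partial exposure. If comparative results have already been seen, label the choice of pairs as post hoc.

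Option (b) needs no new data. Its cost is a few extra exploratory models with the wide intervals shown above.

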Potential participants who meet initial eligibility criteria (aged at least 18 years and an informal caregiver of a person with Alzheimer's disease or related dementias) will be identified through the Utah Caregiver Support Program and the Utah Alzheimer's Association. In addition, the TLC Research Study will be a referral source, providing referrals of previous research participants who agreed to be contacted about future research studies. Recruitment strategies include: 1) announcements and flyers shared via email, program newsletters, social media posts, libraries, pharmacies, and handed out at caregiver support groups, and 2) personal contact by program leadership and research staff, and 3) Opt-out letters sent to previous research studies who agreed to be contacted for future research. Interested individuals will be screened for eligibility based on inclusion/exclusion criteria by the student assistant or the primary investigator. Interested individuals will be invited to a pre-screening interview via phone or in person. This interview will be scheduled at a date and time and location that is convenient for the caregiver. Those who meet the final inclusion criteria will qualify for participation and be invited to take part in the study. The student assistant or the primary investigator will review the IRB-approved informed consent document, which will include a description of voluntary participation, study procedures, risks, and potential benefits. Those who consent will be enrolled in the study.

Enrollment

Randomization: After enrollment, 15 will be randomized to the intervention group and 15 will be randomized to the waitlist control group. Randomization will be done using randomized blocks of size 2, 4, and 6. The allocation table will be uploaded to REDCap for randomization by the study team. This will happen when groups of 10 are enrolled and repeated until 30 are enrolled. The allocation table will be made by a statistician and the people randomizing from REDCap will be blinded from the table.

Time Commitment

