Participants will participate across 14 weeks. Those in Intervention first (Group A) will participate in three caregiver meetings held every two weeks across six weeks. This will be followed by data collection check-ins over 8 weeks. The second group (Group B) will begin with 8 weeks of data collection check-ins, followed by three caregiver meetings over 6 weeks. Each meeting will be scheduled every two weeks and last 60 minutes. Survey check-ins will be repeated six times

Protocol: EnACT RCT

Version: 7/20/2025

and will include completion of a survey via phone or internet. Two weeks after the final intervention meeting, participants will be invited to meet together to discuss thoughts about the caregiver training activities.

Frequency and duration of intervention. EnACT will be offered three times to each person. It will occur every two weeks for a total of three 60-minute sessions. Each participant will be invited to complete one take-home written exercise after session 1 and session 2, which will involve journaling about topics related to the session.

Study assessments for caregivers will include (total time = 95 minutes):

Baseline survey: 20 minutes

Time 2 survey: 15 minutes

Time 3 survey: 15 minutes

Time 4 survey: 15 minutes

Time 5 survey: 15 minutes

Time 6 survey: 15 minutes

Additional time commitments will include:

Study Eligibility Interview: 15 minutes

Final debrief focus group: 60-90 minutes

Reimbursement

Caregivers will receive \$25.00 for each caregiver meeting that they attend, \$10 for the completion of three surveys gathered outside of meetings, and \$50 to attend the final focus group meeting. It is possible to receive \$155.00 total in compensation. Payment will be distributed at the end of the study either through direct deposit or check. You will only be paid for each visit or survey that you complete. If you discontinue early from the study, you will receive a partial amount based on how many meetings and surveys you complete.

Assessment Schedule

Survey data will be gathered at six time points no less than two weeks apart over the course of control, intervention, and follow up.

Focus group data will be gathered during the debrief meeting two weeks after intervention meetings are complete.

Feasibility and Acceptability data will be gathered throughout. Satisfaction surveys will be gathered at the end of each intervention session as part of the session.

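### EnACT is delivered in groups and randomised in batches of 10, but the D1/D2 model names no batch or session-group term, so its D2 intervals ignore shared sessions

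*Combined protocol and SAP*

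**What the plan says.** All references are to the combined protocol and SAP.

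- **Delivery.** Sample Size has participants "randomly assigned to the group-based EnACT intervention" or a waitlist. Time Commitment describes "three caregiver meetings held every two weeks across six weeks" for Group A; Group B has the same number of meetings after its wait. The size and make-up of a meeting group are not given.
- **Randomisation.** Enrollment states that "15 will be randomized to the intervention group and 15 will be randomized to the waitlist control group". It adds: "Randomization will be done using randomized blocks of size 2, 4, and 6". On timing it says: "This will happen when groups of 10 are enrolled and repeated until 30 are enrolled". It also says "The allocation table will be made by a statistician". It does not say whether blocks close at 10 or 30, or whether the list runs on or restarts between batches.
- **Analysis.** The model paragraph, under Feasibility of Outcome Measures, says "the regression controls for baseline measures" and defines D1 (natural change) and D2 (added effect of the intervention). Group B's own treated phase contributes to D2. Alpha is 0.05 and 95% intervals are reported. Neither this paragraph nor the constrained longitudinal analysis in Sample Size names a batch or session-group term, and no ICC is given.

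**The concern.** Caregivers who share three meetings share a leader's session, a discussion and each other. Their outcomes after treatment may be more alike than those of caregivers from different groups. If so, 15 treated people carry less information than 15 independent people, and a model without a group term gives a D2 standard error that is too small.

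Batch is a separate matter. The trial enters people in three batches at different calendar times, and batch is a natural stratum that the model leaves out.

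What is at stake is the Aim 3 output. The plan intends to use direction and magnitude, with 95% intervals, to choose signals for a later, fully powered trial. Intervals that are too narrow make a chance signal look firmer than it is. The next trial would also inherit a plan that does not mention clustering.

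**Working it through.** **1. The plan's own figure.** Sample Size gives power of 0.70 for an effect of 0.5 with N = 30, from simulation. A plain two-group comparison with 15 per arm gives 0.277 two-sided. A baseline-adjusted comparison of the mean of four post-baseline measures (equal correlations assumed) gives 0.65 at correlation 0.6 and 0.73 at 0.7. So 0.70 is attainable, but it cannot be confirmed because the variance, correlation and simulation settings are not given.

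**2. Inputs for clustering.**
- Group size m = 5: inferred from batches of 10 split 1:1; not stated.
- ICC 0.01, 0.05 and 0.10: assumed, on the scale of the model's residual variance; none stated.
- Two-sided 5% test with a normal approximation.

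**3. Formulas.** The variance factor for a clustered arm is 1 + (m − 1) × ICC = 1 + 4 × ICC. At week 8 Group A has had its sessions and Group B is taken as still untreated, so the factor F for the difference is [(1 + 4 × ICC) + 1] / 2. Where both arms have had sessions, F = 1 + 4 × ICC. Actual type I error is 2 × [1 − Φ(1.96 / √F)], and the correct interval is √F times as wide.

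| ICC | Week 8: F | Width | Type I | Both arms: F | Width | Type I |
|---|---|---|---|---|---|---|
| 0.01 | 1.02 | +1% | 5.2% | 1.04 | +2% | 5.5% |
| 0.05 | 1.10 | +5% | 6.2% | 1.20 | +10% | 7.4% |
| 0.10 | 1.20 | +10% | 7.4% | 1.40 | +18% | 9.8% |

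These figures make no allowance for having only about three groups per arm, and they are not a refit of the D1/D2 model.

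Group size matters. If a whole arm of 15 met as one group, which batch entry makes unlikely but the text does not exclude, the both-arm factor would be 1 + 14 × 0.05 = 1.70 or 1 + 14 × 0.10 = 2.40. Type I error would then be about 13% or 21%.

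**4. Effect on the stated power.** Power of 0.70 implies a standard error of 0.5 / (1.96 + 0.524) = 0.201. With F = 1.20, power is Φ(2.484 / 1.095 − 1.96) = 0.62. With F = 1.40, it is Φ(2.484 / 1.183 − 1.96) = 0.56.

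**5. Allocation.** Thirteen ordered sequences of 2, 4 and 6 sum to 10, such as 4+6 or 2+4+4, so the sizes can close at 10. If instead one continuous list is drawn with equally likely sizes (an assumption):
- a block ends exactly at 10 with probability 121/243 = 0.498;
- all three batches are 5:5 in 53% of lists, and some batch is 7:3 in 3.4%;
- the total is 15/15 in 81% and 14/16 or 16/14 in 19%. It is never worse, because a cut block leaves an excess of at most two.

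A 14/16 split keeps 4 × 14 × 16 / 900 = 99.6% of the efficiency of 15/15.

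If the list restarts at each batch, a batch is 5:5 with probability 0.8093 and 6:4 in a given direction with probability 0.0953. The chance of 15/15 is then 0.8093³ + 6 × 0.8093 × 0.0953² = 0.53 + 0.04 = 0.57, with a worst case of 18/12.

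**The case against.** The strongest reply is that this is a feasibility pilot. Statistical Management & Analysis says that such studies cannot settle hypotheses or give reliable effect sizes, and no stated decision turns on an Aim 3 p-value. The size of the clustering effect rests on a group size and an ICC that the documents do not give. This stands, and it limits the weight of the point. It does not remove it, because the plan still reports 95% intervals and uses them to judge what to carry forward.

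Several stronger readings are tempting but not supported:

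- **That blocks of 2, 4 and 6 cannot fit a batch of 10.** They can. What is missing is a statement that they do, and the statistician may have built the table that way.
- **That each batch is treated as a unit, in groups of five, with differences between facilitators.** The batch sentence covers randomisation only, and the documents do not describe facilitators. Groups of about five are a reasonable inference and no more.
- **That uneven batches bias the arm comparison.** Such imbalance is chance. With batches split 6:4, 4:6 and 5:5, a 0.3 SD gap between the two uneven batches moves the arm difference by (2/15) × 0.3 = 0.04 SD, against an unadjusted standard error of √(2/15) = 0.37 SD. Baseline adjustment would absorb part of it.
- **That varying block sizes serve no purpose here.** Their value is smaller when ten people are already enrolled. But if records are randomised one at a time (not stated), a forced 5:5 makes the last assignment in a batch predictable.

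It is also fair to say that the plan gives no covariance structure. The omission is of any named term for batch or group, not an explicit statement of independence.

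**Conclusion.** The point holds as an inexpensive improvement to the Aim 3 analysis. With groups of about 5 and an ICC of 0.05 to 0.10, the week-8 contrast has variance about 10 to 20% above what the model would report, and a nominal 5% test runs at about 6 to 7%. For comparisons in which both arms have had sessions, it runs at about 7 to 10%. With an ICC near 0.01 the effect is negligible; with larger groups it is greater. Because Group B's treated phase also informs D2, the exact inflation for D2 depends on the fitted model, and these figures are indicative. The primary feasibility and acceptability results are not affected.

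The allocation gap is minor and is mainly missing detail. On a continuous list the worst total is 14/16, at almost no cost in efficiency; a list that restarts each batch could reach 18/12.

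**What to change.** 1. **Model.** Add batch (three levels) as a fixed effect in the D1/D2 model. It removes variation shared by both arms of a batch, but not correlation from sharing sessions, so item 2 is still needed.
2. **Sensitivity analysis.** Report D2 with standard errors and 95% intervals inflated for ICCs of 0.05 and 0.10, using the actual session-group sizes. State that about three groups per arm are too few to estimate an ICC reliably. For that reason a fitted group random effect, or an ICC reported from this trial, should not be relied on.
3. **Description.** State the size and composition of the session groups.
4. **Allocation, for any batch not yet randomised.** Use block sequences that sum to 10, such as 4+6 or 2+4+4, so that each batch is 5:5 and the total is 15/15. Randomise all ten together so that the predictable last assignment does no harm.

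The cost is 2 degrees of freedom, slightly wider intervals, and a revised allocation table for any remaining batch. Items 1 to 3 apply even if randomisation is complete.
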